#### **6.6.1.2. Adverse events leading to discontinuation of study drug**

The frequency (number and percentage) of participants with each of the following will be presented for TEAEs leading to discontinuation of each study drug, by treatment arm in Cohort A and by Cohorts B1 and B2, as applicable:

- TEAEs leading to discontinuation of PF-06801591 by SOC and PT
- Related TEAEs leading to discontinuation of PF-06801591 by SOC and PT
- TEAEs leading to discontinuation of BCG by SOC and PT (Cohort A only)
- Related TEAEs leading to discontinuation of BCG by SOC and PT (Cohort A only)
- TEAEs leading to discontinuation of all study drugs by SOC and PT (Cohort A only)
- Related TEAEs leading to discontinuation of all study drugs by SOC and PT (Cohort A only)

The listing of all AEs leading to discontinuation of study drug will also be provided with the relevant information.

#### **6.6.1.3. Adverse events leading to interruption of study treatment**

AEs leading to interruption will be defined as AEs identified in the AE eCRF page with an action taken with study treatment of ‘drug interrupted’.

The frequency (number and percentage) of participants with each of the following will be presented for TEAEs leading to interruption of each study drug by treatment arm in Cohort A:

- TEAEs leading to interruption of PF-06801591 by SOC and PT
- TEAEs leading to interruption of BCG by SOC and PT

The listing of all AEs leading to interruption of study treatment will also be provided with the relevant information for Cohort A and Cohorts B1 and B2.

#### **6.6.2. Deaths**

The frequency (number and percentage) of participants in the safety analysis set who died and who died within 30 days after last dose of study treatment as well as the reason for death, will be tabulated based on information from the 'Notice of Death' eCRF, by treatment arm in Cohort A and by Cohorts B1 and B2.

- All deaths
- Deaths within 30 days after last dose of study treatment
- Deaths due to COVID-19 (if >10% are due to COVID-19)
- Reason for Death
  - Disease under study
  - Study treatment toxicity
  - Unknown
  - Other.

In addition, date and cause of death will be provided in individual participant data listing together with selected dosing information (study treatment received, date of first / last administration, dose) and will include the following information:

- AEs with fatal outcome (list PTs of AEs with outcome=Fatal, as well as AEs of Grade 5),
- Flag for death within 30 days of last dose of study treatment.
- Flag for deaths related to COVID-19.

#### **6.6.3. Serious adverse events**

The frequency (number and percentage) of participants with each of the following will be presented for treatment-emergent SAEs by treatment arm in Cohort A and by Cohorts B1 and B2:

- SAEs by SOC and PT
- Related SAEs by SOC and PT

The listings of all SAEs will also be provided with the relevant information with a flag for SAEs with onset outside of the on-treatment period for Cohort A and Cohorts B1 and B2.

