Urinalysis	X	X*		X						X		X**	Collect sample prior to each BCG administration as indicated, including: *during the re-induction, as applicable (Cycles 4 and 5) **during Cycles 19 and 25. As clinically indicated during other cycles. See Section 10.2 for the list of the tests.
Pregnancy Test	X	X	X	X	X	X	X	X	X	X	X	X	A negative highly sensitive test is required prior to study intervention dosing on Day 1 of all cycles. Results must be available for review prior to dosing. See Section 8.2.8 and Section 10.4. Pregnancy testing per local guidelines.
ACTH & Thyroid Function Test			X			X			X			X*	*Completed on Day 1 of Cycles 15, 18, 21, 24, 25.
BCG Administration (Arms A & C)	X*#	X*		X#						X#		X#	Follow calendar cycle for dosing, not the schedule. See Section 6.1.2 for details. On days when BCG and PF-06801591 are both administered, BCG is administered first. *Re-induction period: See Section 4.1 for participants who may meet criteria for re-induction. Suggested instillations on C4D1, C4D8, C4D15, C4D22, C5D1, and C5D8. Maintenance will then begin on C7D1. If TURBT is performed, BCG re-induction schedule should be modified according to the product label. #Maintenance BCG schedule: D1, D8, D15 of Cycles 4, 7, 13, 19, and 25.
PF-06801591 Administration (Arms A & B)	X	X	X	X	X	X	X	X	X	X	X	X	Administer subcutaneously Q4W up to Cycle 25. See Section 6.1.2.

Maintenance Period: Cycles 4 to 25 (Cycle = 4 Weeks) for participants without re-induction BCG Re-induction Period for Participants Who Receive BCG Re-induction: Cycles 4-6 ; Maintenance Period: Cycles 7 to 25													
	C4D1	C5D1	C6D1	C7D1	C8D1	C9D1	C10D1	C11D1	C12D1	C13D1	C14D1	C15D1 thru C25D1	Notes
Visit Window (Days)	±7	±7	±7	±7	±7	±7	±7	±7	±7	±7	±7	±7	
Disease Assessments													
CT or MRI	As clinically indicated												
Cystoscopy with or without Biopsy	X			X			X			X		X*	Participants with CIS at randomization who do not achieve a CR within 6 months of initiating study intervention will discontinue study treatment and enter the post-treatment follow-up period. Cystoscopy with or without tumor biopsy; ±7 days allowed for on-treatment assessment. Same equipment and methods by the same study staff should be used for the duration of the study whenever possible. See Section 8.1.1.1. * Completed every 12 weeks.

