8.3.1. Time Period and Frequency for Collecting AE and SAE Information

The time period for actively eliciting and collecting AEs and SAEs (“active collection period”) for each participant begins from the time the participant provides informed consent, which is obtained before the participant’s participation in the study (ie, before undergoing any study-related procedure and/or receiving study intervention), through and including a minimum of 90 calendar days after the last administration of the study intervention.

For participants who are screen failures, the active collection period ends when screen failure status is determined.

Follow-up by the investigator continues throughout and after the active collection period and until the AE or SAE or its sequelae resolve or stabilize at a level acceptable to the investigator and Pfizer concurs with that assessment.

For participants who are screen failures, the active collection period ends when screen failure status is determined.

If the participant withdraws from the study and also withdraws consent for the collection of future information, the active collection period ends when consent is withdrawn.

If a participant definitively discontinues or temporarily discontinues study intervention because of an AE or SAE, the AE or SAE must be recorded on the eCRF and the SAE reported using the CT SAE Report Form.

Investigators are not obligated to actively seek AEs or SAEs after the participant has concluded study participation. However, if the investigator learns of any SAE, including a death, at any time after a participant has completed the study, and he/she considers the event to be reasonably related to the study intervention, the investigator must promptly report the SAE to Pfizer using the CT SAE Report Form.

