##### **Start and end dates of study treatment:**

For Arm A and Arm B in Cohort A:

The date/time of first dose of study treatment in a combination arm is the earliest date/time of the first non-zero dose date/time for any of the study drugs in the combination.

The date/time of last dose of study treatment in a combination arm is the latest date/time of the last non-zero dose date/time for any of the study drugs in the combination.

For Arm C (BCG only) in Cohort A and Cohorts B1 and B2 (PF-06801591 only):

The date/time of first dose of study treatment is the earliest date/time of non-zero dosing of the study drug.

The date/time of last dose of study treatment is the latest date/time of non-zero dosing of the study drug.

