### **5.2.7. Definition of on-treatment period**

Safety endpoints will be summarized based on the on-treatment period unless otherwise specified.

On-treatment period is defined as the time from the first dose of study treatment through minimum (30 days + last dose of study treatment, start day of new anti-cancer drug therapy – 1 day) (also refer to Appendix 1 for irAEs).

Safety data collected outside the on-treatment period as described above will be listed and flagged in listings but will not be summarized.

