#### **For BCG:**

Dosing in each period will be determined by the CRF disposition pages for when each period started and ended based on when participants started the next period.

- Induction: Dose Delay for Dose x (days) = Date of Dose x – Date of Dose (x-1) – 7,
- Re-induction: Dose Delay for Dose x (days) = Date of Dose x – Date of Dose (x-1) – 7,
- Maintenance:

Dose Delay for Dose x (days) = Date of Dose x – Date of Dose (x-1) – 7, for doses within a cycle (i.e. between Days 1, 8, and 15 of Cycle 4, Cycle 7, Cycle 13, Cycle 19 and Cycle 25).

Dose Delay for Dose x (days) = Date of Dose x – Date of Dose (x-1) – 70, between the last dose of the cycle prior to Cycle 7 and next dose (i.e. between Cycle 4 Day 15 to

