### Cycle 7 Day 1)

Dose Delay for Dose x (days) = Date of Dose x – Date of Dose (x-1) – 154, between the last dose of the previous cycle (Cycle 7 and after) and next dose (i.e. between maintenance cycles 7 to 25 from Day 15 to Day 1 (i.e. Cycle 7 Day 15 to Cycle 13 Day 1)

For Cohort A, dose delays will be grouped into the following categories, Cycles 1-3 and Cycle 4-25, for both BCG and PF-06801591.

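### The by-arm SAE tables close at last dose + 30 days or at new anti-cancer drug therapy, so later non-fatal SAEs outside the irAE definitions appear only in listings; for some stops this cut-off falls earlier in Arm C

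*SAP*

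**What the plan says.** **The tables.** SAP 6.6.3 plans two tables, all SAEs and related SAEs, each by SOC and PT: "The frequency (number and percentage) of participants with each of the following will be presented for treatment-emergent SAEs by treatment arm". SAP 3.5.1 and 5.2.7 end the on-treatment period at the earlier of last dose + 30 days and the day before new anti-cancer drug therapy. On later data SAP 5.2.7 says: "Safety data collected outside the on-treatment period as described above will be listed and flagged in listings but will not be summarized". SAP 6.6.3 also provides a listing of every SAE, with a flag for onset outside the window.

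**Collection.** Protocol 8.3.1 collects SAEs "through and including a minimum of 90 calendar days after the last administration of the study intervention". Protocol 8.3.1.2 keeps SAE recording on the eCRF going for that period after new anticancer therapy begins. The Cohort A follow-up schedule in Protocol 1.3 has safety visits 30, 60 and 90 days after EOT, where EOT can follow either the last dose or the decision to stop both drugs. AEs are collected at these visits. Treatment-related SAEs are also reported during disease and survival follow-up.

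**What already reaches past the cut-off by arm.** SAP 6.6.4.1 and Table 25 Step 2 count irAEs, serious irAEs and potential irAEs to 90 days after last dose regardless of new therapy. SAP 6.6.2 counts all deaths with reason.

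**What sets last dose.** In Arms A and B it is the later of the two drugs (SAP 3.4.1). In Arm C only BCG counts: "The date/time of last dose of study treatment is the latest date/time of non-zero dosing of the study drug". For PF-06801591, Protocol 1.3 says: "Administer subcutaneously Q4W up to Cycle 25". For BCG maintenance, SAP 6.5.3.4 sets a planned interval of 70 days "between the last dose of the cycle prior to Cycle 7 and next dose", and for later blocks it gives "154, between the last dose of the previous cycle (Cycle 7 and after) and next dose".

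**The concern.** The safety objective describes AEs by seriousness, timing and relationship. A by-arm SAE percentage that stops at 30 days leaves out events that sites are required to record. A reader who wants the fuller count must build it from a flagged listing. Thirty days is also not long for this antibody. Protocol 2.2.1 gives a half-life of about 13 days, so by simple halving 0.5^(30/13), about 20%, remains at day 30.

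The second issue is comparability. The cut-off runs from the last non-zero dose, and the arms are dosed at different intervals. A participant who stops in a long BCG gap in Arm C can have the window close before the decision to stop is made. An SAE on the same calendar day could then be tabulated in Arms A and B but not in Arm C.

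**Working it through.** **Day convention.** CnDx = (n − 1) × 28 + x.

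**Reproducing the plan's intervals.**
- C4D15 = 99 and C7D1 = 169; 169 − 99 = 70 days.
- C7D15 = 183 and C13D1 = 337; 337 − 183 = 154 days.

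Both match SAP 6.5.3.4.

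**Length of the gap.** Days 31 to 90 after last dose are 60 of the 90 days of minimum collection (67%), and more if new drug therapy starts before day 30.

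As a share of calendar time from first dose to last dose + 90 (time, not events):
- Completer, Arm B: last dose C25D1 = 673; 60/763 = 7.9%.
- Completer, Arms A and C: last dose C25D15 = 687; 60/777 = 7.7%.
- Stop for no CR at week 24. The rule in Protocol 1.3 is "Participants with CIS at randomization who do not achieve a CR within 6 months of initiating study intervention will discontinue study treatment". With last PF-06801591 dose at C6D1 = 141: 60/231 = 26.0%.
- Same stop in Arm C after re-induction, last BCG at C5D8 = 120: 60/210 = 28.6%.
- Upper end: last dose on day 141 and new drug therapy on day 162, the earliest in-window assessment day. The window closes on day 161; 70/231 = 30.3%.

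**Cut-off by arm (last dose + 30).** Assumptions: planned dosing, no re-induction, no new drug therapy, PF-06801591 still being given in Arms A and B, and a stop decided before that day's dose.

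| Stop | Arms A, B: last dose → cut-off | Arm C: last dose → cut-off | Difference |
|---|---|---|---|
| C10D1 (day 253) | 225 → 255 | 183 → 213 | 42 days |
| C13D1 (day 337) | 309 → 339 | 183 → 213 | 126 days |

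In Arm C the window has closed 253 − 213 = 40 days before the first stop and 337 − 213 = 124 days before the second. In Arms A and B, 28-day dosing against a 30-day tail keeps the window open 2 days past the stop.

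**Completers.** Arms A and C: 687 + 30 = 717. Arm B: 673 + 30 = 703, so Arm B closes 14 days earlier.

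**Which longer window helps.**
- Last dose + 90 leaves the arm difference unchanged. At C10D1 it ends on day 273 in Arm C and 315 in Arms A and B. At C13D1 it ends on day 273 and 399, and Arm C still closes 337 − 273 = 64 days before the stop.
- EOT + 90, with EOT on the decision day, gives 253 + 90 = 343 and 337 + 90 = 427 in every arm. These are later than last dose + 90, so they would govern. The 7-day allowance for the EOT visit can move each by up to a week.

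**The case against.** The strongest reply is that this is a deliberate and consistent choice. Protocol 9.4.2 states the same window, and the analysis is descriptive. Stopping at new drug therapy avoids charging its toxicity to the randomized arm. The main class risk is handled by the 90-day irAE tables, deaths are counted at any time, and every remaining event is listed. All of this stands, and it is why the severity is low. It does not supply a by-arm count of the remaining SAEs, and the SAP already accepts a 90-day window regardless of new therapy for irAEs.

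The arm difference is also conditional. It arises for stops between BCG blocks while PF-06801591 continues in Arms A and B. Protocol 7.1 lets one drug be stopped alone, so an Arm A participant left on BCG only has the Arm C cut-off. This also stands.

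A reader might infer more than the documents support:
- **That the SAP contradicts the protocol.** It does not: it follows the protocol default, which Protocol 9.4.2 allows the SAP to change.
- **That late SAEs are lost.** They are recorded, listed and flagged.
- **That the window hides harm of PF-06801591 relative to control.** For stops in a BCG gap, it is control-arm SAEs that go uncounted, which would make Arms A and B look relatively worse.
- **That Arm C always closes first.** Among completers it is Arm B.

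**Conclusion.** The point holds as a reporting gap. After the cut-off, non-fatal SAEs outside the irAE definitions have no by-arm count, although they are recorded for at least 90 days and treatment-related SAEs are reported for longer. The primary and key secondary analyses are untouched.

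The documents give neither late SAE rates nor early-stop rates, so the number of affected events cannot be estimated. What can be shown is the length of the untabulated time (about 8% for a completer and 26% to 30% for a no-CR stop at week 24) and the 42-day and 126-day differences in cut-off for the two example stops. These rest on the planned schedule and the assumptions listed with them. Low severity; a cheap improvement.

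**What to change.** Keep the TEAE tables as they are. In SAP 6.6.3, add supplementary by-arm Cohort A tables of all SAEs and related SAEs by SOC and PT. Count onset from first dose through the later of last dose + 90 days and EOT + 90 days, regardless of new anti-cancer drug therapy. The EOT anchor largely removes the arm difference for stops inside a BCG gap; the 14-day completer difference follows from the dosing schedule and remains.

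Also:
- Flag events with onset after subsequent therapy.
- Flag fatal-malignancy Grade 5 SAEs, which Protocol 10.3.2 requires to be recorded as SAEs.
- Give a by-arm count of treatment-related SAEs reported after the window.
- Add an exception for these tables to the last sentence of SAP 5.2.7.

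**Cost.** Two tables, one count, two flags and one amended sentence, from data already recorded and listed. No protocol amendment is needed. The downside is that some late events will reflect progression or later therapy, hence the flags. Where EOT + 90 extends beyond last dose + 90, the data rest on the scheduled safety visits, because Protocol 8.3.1 guarantees only the 90 days from last dose. A footnote should say so.

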#### **6.6.4. Other significant adverse events**

Adverse events of special interest in this study are immune-related adverse events and injection site reactions.

##### **6.6.4.1. Immune related adverse events**

The criteria for classification of an adverse event as an irAE is described in Appendix 1. The frequency (number and percentage) of participants with each of the following will be presented for irAEs, by treatment arm in Cohort A and by Cohorts B1 and B2, if applicable:

- irAEs leading to death, by Cluster and PT (Cohort A only)
- irAEs, by Cluster, PT, and worst Grade
- irAEs, Any Grade and Grade  $\geq 3$ , by Cluster and PT (Cohort A only)
- irAEs leading to discontinuation of PF-06801591, by Cluster and PT
- irAEs leading to discontinuation of BCG, by Cluster and PT (Cohort A only)
- irAEs leading to discontinuation of all study drugs, by Cluster and PT (Cohort A only)
- Serious irAEs, by Cluster and PT

The listing of all irAEs will also be provided with the relevant information with a flag for irAEs with onset outside of the on-treatment period for irAE (i.e., irAEs not meeting the programmatic criteria in Step 2 as outlined in Table 25 of Appendix 1)

The frequency (number and percentage) of participants with potential irAEs (i.e., AEs meeting the programmatic criteria Step 1 and Step 2 outlined in Table 25 of Appendix 1) will also be presented by treatment arm in Cohort A and by Cohorts B1 and B2.

##### **6.6.4.2. Injection site reactions related to PF-06801591**

The frequency (number and percentage) of participants with the following will be presented by treatment arm in Cohort A and by Cohorts B1 and B2

- ISRs related to PF-06801591 by HLT, PT, and worst grade

#### **6.6.5. Laboratory data**

Summaries of laboratory data will be based on the safety analysis set by treatment arm in Cohort A. For Cohorts B1 and B2 only listings will be provided.

##### **6.6.5.1. Hematology and chemistry parameters**

Laboratory results will be classified according to the CTCAE v5.0. Non-numerical qualifiers (with the exception of fasting flags) will not be taken into consideration in the derivation of

CTCAE criteria. Additional laboratory results that are not graded per CTCAE v5.0 will be presented according to the categories: below normal limit, within normal limits and above normal limit (according to the laboratory normal ranges).

Quantitative data will be summarized using simple descriptive statistics (mean, SD, median, Q1, Q3, minimum, and maximum) of actual values and changes from baseline for each nominal visit over time (unscheduled measurements would therefore not be included in these summaries as described in [Section 5.2.9](#)). End of Treatment visit laboratory results will be summarized separately. The changes computed will be the differences from baseline. Qualitative data based on reference ranges will be described according to the categories (i.e., Low, Normal, High).

Abnormalities classified according to CTCAE v5.0 will be described using the worst grade. For those parameters which are graded with two toxicities, the toxicities will be summarized separately.

Low direction toxicity grades at baseline and post baseline will be set to 0 when the variables are derived for summarizing high direction toxicity, and vice versa.

For **WBC differential counts** (total neutrophil [including bands], lymphocyte, monocyte, eosinophil, and basophil counts), the absolute value will be used when reported. When only percentages are available (this is mainly important for neutrophils and lymphocytes, because the CTCAE grading is based on the absolute counts), the absolute value is derived as follows:

$$\text{Derived differential absolute count} = (\text{WBC count}) \times (\text{Differential \%value} / 100)$$

If the range for the differential absolute count is not available (only range for value in % is available) then Grade 1 will be attributed to as follows:

- Lymphocyte count decreased:
  - derived absolute count does not meet Grade 2-4 criteria, and
  - % value < % LLN value, and
  - derived absolute count  $\geq 800/\text{mm}^3$
- Neutrophil count decreased
  - derived absolute count does not meet Grade 2-4 criteria, and
  - % value < % LLN value, and
  - derived absolute count  $\geq 1500/\text{mm}^3$

For **calcium**, CTCAE grading is based on Corrected Calcium and Ionized Calcium (CALCIO). Corrected Calcium is calculated from Albumin and Calcium as follows

$$\text{Corrected calcium (mmol/L)} = \text{measured total Calcium (mmol/L)} + 0.02 (40 - \text{serum albumin [g/L]})$$

**Liver function tests:** Alanine aminotransferase (ALT), aspartate aminotransferase (AST), alkaline phosphatase (ALP), and total bilirubin (TBIL) are used to assess possible drug induced liver toxicity. The ratios of test result over upper limit of normal (ULN) will be calculated and classified for these three parameters during the on-treatment period.

Summary of liver function tests will include the following categories. The number and percentage of participants with each of the following during the on-treatment period will be summarized by treatment arm in Cohort A and by Cohorts B1 and B2:

- ALT  $\geq 3 \times$ ULN, ALT  $\geq 5 \times$ ULN, ALT  $\geq 10 \times$ ULN, ALT  $\geq 20 \times$ ULN
- AST  $\geq 3 \times$ ULN, AST  $\geq 5 \times$ ULN, AST  $\geq 10 \times$ ULN, AST  $\geq 20 \times$ ULN
- (ALT or AST)  $\geq 3 \times$ ULN, (ALT or AST)  $\geq 5 \times$ ULN, (ALT or AST)  $\geq 10 \times$ ULN, (ALT or AST)  $\geq 20 \times$ ULN
- TBIL  $\geq 2 \times$ ULN
- Concurrent ALT  $\geq 3 \times$ ULN and TBIL  $\geq 2 \times$ ULN
- Concurrent AST  $\geq 3 \times$ ULN and TBIL  $\geq 2 \times$ ULN
- Concurrent (ALT or AST)  $\geq 3 \times$ ULN and TBIL  $\geq 2 \times$ ULN
- Concurrent (ALT or AST)  $\geq 3 \times$ ULN and TBIL  $\geq 2 \times$ ULN and ALP  $> 2 \times$ ULN
- Concurrent (ALT or AST)  $\geq 3 \times$ ULN and TBIL  $\geq 2 \times$ ULN and (ALP  $\leq 2 \times$ ULN or missing)

Concurrent measurements are those occurring on the same date.

Categories will be cumulative, i.e., a participant with an elevation of AST  $\geq 10 \times$ ULN will also appear in the categories  $\geq 5 \times$ ULN and  $\geq 3 \times$ ULN. Liver function elevation and possible Hy's Law cases will be summarized using frequency counts and percentages.

An evaluation of Drug-Induced Serious Hepatotoxicity (eDISH) plot will also be created, with different symbols for different treatment arms, by graphically displaying

- peak serum ALT(/ULN) vs peak total bilirubin (/ULN) including reference lines at ALT= $3 \times$ ULN and total bilirubin= $2 \times$ ULN.
- peak serum AST(/ULN) vs peak total bilirubin (/ULN) including reference lines at AST= $3 \times$ ULN and total bilirubin= $2 \times$ ULN.

In addition, a listing of all TBIL, ALT, AST and ALP values for participants with concurrent (ALT or AST)  $\geq 3 \times$ ULN and TBIL  $\geq 2 \times$ ULN and (ALP  $\leq 2 \times$ ULN or missing) will be provided.

